#### **Lumpectomy PTV Eval:**

- $\geq 95\%$  of the Lumpectomy PTV Eval will receive  $\geq 4819$  cGy which is 95% of the cumulative boost prescribed dose of 5073 cGy
- $\leq 5\%$  of the Lumpectomy PTV Eval will receive  $\geq 5580$  cGy which is 110% of the boost prescribed dose of 5073 cGy
- Maximal point dose will be  $\leq 5834$  cGy which is 115% of the boost prescribed dose of 5073 cGy

#### **Supraclavicular (SCV):**

- $\geq 95\%$  of the SCV PTV will receive  $\geq 95\%$  of the prescribed dose of 4005 cGy
- Maximal point dose (to  $>0.1\text{cc}$ ) will be  $\leq 4606$  cGy which is 115% of the SCV prescribed dose of 4005 cGy

**Axillary volume (undissected):**

- $\geq 95\%$  of the Axillary PTV will receive  $\geq 95\%$  of the prescribed dose of 4005 cGy
- Maximal point dose will be  $\leq 4406$  cGy which is 110% of the Axillary prescribed dose of 4005 cGy

**Internal mammary nodal (IMN) volumes (optional):**

- $\geq 90\%$  of the IMN PTV will receive  $\geq 90\%$  of the prescribed dose of 4005 cGy
- Maximal point dose will be  $\leq 4406$  cGy which is 110% of the IMN prescribed dose of 4005 cGy

**Normal Tissue Constraints****Contralateral breast:**

- *Per Protocol:* < 5% receives 300 cGy
- *Variation Acceptable:* < 5% receives 410 cGy

**Ipsilateral lung:**

- *Per Protocol:*  $\leq 30\%$  of the ipsilateral lung should receive  $\geq 20$  Gy
  - *Variation Acceptable:*  $\leq 35\%$  of the ipsilateral lung should receive  $\geq 20$  Gy
- *Per Protocol:*  $\leq 50\%$  of the ipsilateral lung should receive  $\geq 10$  Gy
  - *Variation Acceptable:*  $\leq 60\%$  of the ipsilateral lung receives  $\geq 10$  Gy
- *Per Protocol:*  $\leq 65\%$  of the ipsilateral lung should receive  $\geq 5$  Gy
  - *Variation Acceptable:*  $\leq 70\%$  of the ipsilateral lung receives  $\geq 5$  Gy

**Contralateral lung:**

- *Per Protocol:*  $\leq 10\%$  of the contralateral lung should receive  $\geq 5$  Gy
  - *Variation Acceptable:*  $\leq 15\%$  of the contralateral lung should receive  $\geq 5$  Gy

**Heart:**

- *Per Protocol:*  $\leq 5\%$  of the whole heart should receive  $\geq 25$  Gy for left-sided breast cancers, and 0% of the heart should receive  $\geq 25$  Gy for right-sided breast cancers
  - *Variation Acceptable:*  $\leq 5\%$  of the whole heart should receive  $\geq 30$  Gy for left-sided breast cancers, and 0% of the heart should receive  $\geq 30$  Gy for right-sided breast cancers
- *Per Protocol:*  $\leq 30\%$  of the whole heart should receive  $\geq 15$  Gy for left-sided breast cancers, and  $\leq 10\%$  of the heart should receive  $\geq 15$  Gy for right-sided breast cancers
  - *Variation Acceptable:*  $\leq 35\%$  of the whole heart receives  $\geq 15$  Gy for left-sided breast cancers, and  $\leq 15\%$  of the heart receives  $\geq 15$  Gy for right-sided breast cancers
- *Per Protocol:* Mean heart dose should be  $\leq 4$  Gy
  - *Variation Acceptable:*  $\leq 5$  Gy. Every attempt should be made to make the cardiac exposure to radiation as low as possible.

**Skin bolus**

Skin bolus is not allowed for the treatment of intact breast patients post lumpectomy. The use of skin bolus for post-mastectomy irradiation is per the treating physician's discretion. If using bolus, the skin dose should follow the same constraints as the Chest wall PTV Eval. Verification of clinical skin dose is with nanoDot™ dosimeter (or similar) is encouraged.

## **Treatment verification**

### ***Before first treatment***

Imaging of each 3DCRT beam must be obtained and approved by a physician prior to initiation of treatment. Standard QA and pretreatment IGRT or patient positioning is similarly required for all IMRT cases.

### ***Subsequent images or films***

Subsequent treatment verification will be as per departmental standards, but minimally every 5 fractions. The imaging modality and process should be performed based on the institutional guidelines.

### ***Documentation requirements***

All films or images are to be maintained at the local facility.

## **Baseline and Follow-Up Procedures**

Patients will be seen in follow up as clinically recommended; evaluation for protocol specified data points will at baseline prior to radiation initiation and during specified follow up visits at 6, 12, 36, and 60 months from completion of radiotherapy, to monitor for disease recurrence and treatment-related toxicity. The following should be completed prior to RT (baseline) and at the 6, 12, 36, and 60 month visits. Note that a study calendar can be found at the end of this protocol (Appendix A). In accordance with NCCN guidelines mammography of any remaining intact breast will be performed once every 12 months, though in the absence of clinical signs and symptoms suggestive of recurrent disease, there is no indication for laboratory or imaging studies for metastases screening.

- History and Physical Exam
  - Each per-protocol follow-up encounter will include an interview with a study clinician to elicit signs and symptoms of disease recurrence or treatment-related toxicity. This encounter should include a focused physical exam to include, at minimum, a bilateral breast/chest wall, lymph node, and upper extremity exam, including weight. Height captured at screening only.
- Grading of toxicity
  - All toxicity noted by the study clinicians should be documented at baseline, during weekly visits while receiving radiation, and at each per-protocol follow-up visit (6, 12, 36, and 60 months). Toxicity should be described and graded using the National Cancer Institute's Common Terminology Criteria for Adverse Events (CTCAE) version 4.03. Study clinicians should also comment on the persistence or resolution of toxicity documented at the previous encounter.
- Lymphedema
  - An increase in inter limb arm circumference of at least 10% in the lower arm or the upper arm, or both, compared with the contralateral arm at the same time point, will be judged to be clinically significant lymphedema and recorded as one of the composite adverse events per the primary endpoint of this study. Arm circumference 15 cm above the medial epicondyle (upper arms) and 15 cm below the medial epicondyle (lower arms) will be measured prior to radiotherapy (baseline) and at 6, 12, 36, and 60 months by clinicians.
  - Lymphedema, if present, should also be graded according to CTCAE v4.03 though this grade will not be scored as per the primary endpoint.

- Shoulder mobility
  - Patients will take quality of life questionnaire EORTC QLQ-C3014 and breast-cancer module (BR23) prior to radiotherapy (baseline) and at 6, 12, 36, and 60 months. This questionnaire includes specific items relating to shoulder mobility, particularly item #49 – “During the past week, was it difficult to raise your arm or to move it sideways?”. Responses to all items are on a four-point scale with 1-‘Not at All’, 2-‘A Little’, 3-‘Quite a Bit’, 4-‘Very Much’. Responses to item #49 of 3 or 4 will be scored as decreased shoulder mobility as was done in the START trials.
  - Clinicians should also use a goniometer to measure *bilateral* shoulder mobility in four excursions: abduction, adduction, anteversion, and retroversion. These goniometric measurements will be recorded prospectively prior to radiotherapy (baseline) and at 6, 12, 36, and 60 months, but will not factor into the primary composite endpoint.
- Thyroid function – Thyroid stimulating hormone levels will be required to be drawn prior to radiotherapy (baseline) and at 12, 36, and 60 months. Of course, TSH may also be monitored by other members of the patient’s care team (outside of study clinicians), though this is not a requirement of the study. The proportion of patients with increased TSH levels or requiring a new start of thyroid replacement medication will be reported as a percent
- Radiation effects on reconstructed breast tissue – In patients for whom a tissue-expander is placed at the time of mastectomy to facilitate eventual breast implantation, the rate of expander compromise requiring revision or removal will be prospectively recorded. This rate will be expressed as a percent.
- Quality of Life and Body Image
  - Patients will take quality of life questionnaire EORTC QLQ-C3014 and breast-cancer module (BR23) prior to radiotherapy (baseline) and at 6, 12, 36, and 60 months. This questionnaire was developed by the European Organization for Research and Treatment of Cancer to assess quality of life in cancer patients. This validated, patient-reported measure has been used in multiple prospective breast cancer studies.

## Monitoring and Oversight

### Oversight.

The Lead Principal Investigator (Lead PI) will be responsible for monitoring the trial per the trial monitoring plan, in addition to overseeing the safety and efficacy of the trial, executing the DSM plan, and complying with all reporting requirements to local and federal authorities. This oversight will be accomplished through additional oversight from the Data and Safety Monitoring Committee (DSMC) at the University of Colorado Cancer Center (CU Cancer Center). The DSMC is responsible for ensuring data quality and patient safety for all clinical studies at the CU Cancer Center. A summary of the DSMC’s activities is as follows:

- Conduct of internal audits
- Ongoing review of all serious adverse events (SAEs), unanticipated problems (UAPs) and reportable adverse events (AEs)
- Has the authority to close and/or suspend trials for safety or trial conduct issues
- May submit recommendations for corrective actions to the CU Cancer Center’s Executive Committee

Per the CU Cancer Center Institutional DSM Plan, SAEs, UAPs and reportable AEs are reported to the DSMC, IRB and the sponsor per study protocol. All SAEs, UAPs and reportable AEs are to be reported to the DSMC within 5 business days of receiving notification of the occurrence.

Each subject's treatment outcomes will be discussed by the Investigators and Clinical Research Coordinators (CRCs) at regularly scheduled disease-oriented working group meetings. Data regarding number of subjects, significant toxicities, dose modifications, and treatment responses will be discussed and documented in the meeting's minutes.

The Lead PI will provide a DSM report to the CU Cancer Center DSMC on a six month basis. The DSM report will include a protocol summary; current enrollment numbers; summary of toxicity data to include specific SAEs, UAPs and AEs; any dose modifications; all protocol deviations; and protocol amendments. The DSM report to the DSMC will also include, if applicable, the results of any efficacy data analysis conducted, as well as any internal DSMB reports. Results and recommendations from the review of this six month report by the DSMC will then need to be submitted by the site to the IRB of record at the time of continuing review.

As the Lead PI in this multi-site trial, the Lead PI is responsible for organizing and conducting monthly teleconferences with all participating sites. The Lead PI will also be responsible for including data from all of the participating sites within the overall trial's six month DSM report to the DSMC to include minutes from monthly PI teleconferences. Each participating site will be responsible for submitting the results and recommendations from the DSMC's six month review to their IRB of record at the time of continuing review.

### **Study Monitoring and Frequency of Monitoring Visits**

The monitoring for this trial will be carried out in full compliance with all Good Clinical Practice (GCP) Guidelines, COMIRB policies and regulations and all applicable federal regulations . This study will be monitored for its entire duration until the investigation is completed.

A site initiation visit (SIV) will be conducted for all participating sites prior to enrolling any subjects into this trial to document full training of all study personnel who will be delegated any specific task on the study. This visit includes but is not limited to training on the IRB approved study protocol, regulatory requirements for study conduct including but not limited to GCP guidelines, reporting of adverse events, the review of study personnel's roles and responsibilities, completion of the Delegation of Authority Log and Protocol Training, review of the monitoring plan as outlined in the protocol, and to review data collection and proper source documentation procedures.

The monitor will perform both on-site interim monitoring visits and remote monitoring off-site for all participating sites in this study. Data that is collected during the duration of this trial will be reviewed by the sponsor to identify data discrepancies, inconsistencies or any unclear information both on-site and remotely. In order to reconcile data discrepancies, queries will be sent electronically to the site(s) for data that requires clarification.

Due to the nature of this trial being an interventional radiation Phase II trial, as well as a multi-center IIT (Investigator-Initiated Trial) with the CU Cancer Center as the coordinating site, this study is considered to be high risk and will need consistent routine monitoring visits. An initial monitoring visit will be performed within 2-4 weeks of the first subject being enrolled into the trial. Subsequently, this study will then be monitored every 8-12 weeks on-site, with remote monitoring in-between scheduled on-site visits, as necessary based on the study needs, at all participating sites.

The monitor will perform routine on-site monitoring visits that include but are not limited to:

- Interface with the Principal Investigator at each visit if possible, to discuss any findings, address concerns, and to update the PI and site staff on current study progress.
- Subject source documentation verification and subject eligibility
- Informed Consent review
- Verify radiation treatment
- Protocol adherence
- Review Case Report Forms and the electronic database
- Regulatory documents review
- Review and determine if all Adverse Events and Serious Adverse Events have been appropriately reported within the specified time periods required by the protocol, GCP, the IRB and any other applicable regulatory requirements

After monitoring visits are completed, the monitor will evaluate and summarize the results after each monitoring visit in a written report. This report will include all pertinent findings during the monitoring visit including all identifiable and reportable data and non-compliant problems ongoing in the study and recommend resolutions for noted deficiencies. Any noted deficiencies that are in need of resolution will need a corrective plan of action by the Investigator and/or research staff.

The Investigator will receive a post interim monitoring visit follow-up letter 7 to 10 business days following the completion of the monitoring visit, documenting study progress and any pertinent findings and outstanding action items that need to be resolved. The Investigator will need to sign and date the letter after reviewing, and keep the original on site. The Monitor may review the letter at the next subsequent visit to ensure it has been reviewed, signed and dated by the Investigator in a timely manner.

Upon completion or termination of the study, the sponsor will ensure that each participating site undergo a site Close-out Monitoring visit prior to final closure of the study. The Monitor will assure that all necessary site close-out procedures and activities have been completed which include but are not limited to query resolution, Case Report Form completion, notification to local IRB and regulatory authorities of study closure, record retention arrangements finalized, AE and SAE resolution, and all essential documents are available and present in the Principal Investigator's file. The Monitor will complete a final close-out report documenting completion of the Close-out Monitoring visit and forward a study Close-out follow up letter to the Investigator(s) at the participating site(s) to be reviewed, signed and dated, and file a copy on site for record retention.

#### **Safety and Adverse Event Reporting.**

Any Grade 4 or 5 toxicity by CTCAE will qualify as a serious adverse event (SAE). Brachial plexopathy Grade 2 ('moderate symptoms; limiting instrumental ADL') or Grade 3 ('severe symptoms; limiting self-care ADL') and Grade 3 lymphedema ('Severe symptoms; limiting self-care ADL') will qualify as reportable adverse events (AE).

After the first year, adverse events will only be reviewed at the time of per-protocol follow-up visits by study clinicians. Only Grade 3 and higher will be collected and reported.

Retroactive chart reviews are not necessary unless there is an SAE that is identified that had not otherwise been reported.

All **serious adverse events** should be reported to the site research coordinator, site PI, and the study PI, [name] at [contact].

All serious adverse events will be reported to the COMIRB at the University of Colorado Anschutz Medical Campus according to institutional guidelines, and to the CU Cancer Center DSMC, as stated herein.

The definition of serious adverse event (experience) also includes important medical event. Medical and scientific judgment should be exercised in deciding whether expedited reporting is appropriate in other situations, such as important medical events that may not be immediately life-threatening or result in death or hospitalization but may jeopardize the patient or may require intervention to prevent one of the other outcomes listed in the definition above. These should also usually be considered serious.

The definition of “related” being that there is a reasonable possibility that the RT caused the adverse experience.

An adverse event is UNEXPECTED when the specificity or severity is not consistent with the current expectations of biopsy complications being extremely uncommon.

## **Data Security**

### Paper records:

All paper records containing the patient’s information will be stored in a locked file in a secure location in the Department of Radiation Oncology. Only members of the research team will have access to these records.

### Electronic records:

Study data will be collected and managed using an electronic database. The database will be a secure system with audit capabilities.

All study related electronic files will only be made available to personnel involved in the study through the use of access privileges and passwords.

## **E. Potential Scientific Problems:**

As with any prospective, single-institution study, sufficient patient accrual is a potential scientific problem that may limit statistical power. Over the last two years, we have treated 142 potentially eligible patients at the University of Colorado Denver. While some eligible patients will undoubtedly decline enrollment, we do expect this study to be particularly attractive to patients given that the proposed treatment is two weeks shorter than standard therapy. It is estimated that this trial will accrue, on average 8 patients per month over all sites, 5 patients per month at the UC Denver campus, and 1-2 patients per month at North and South campuses. Based on our required sample size of 106 patients (justification below), it will take approximately 18-22 months to complete accrual once the study is open at all three campuses.. The primary endpoint will be reported after all patients have been followed for one year.

Accrual.

If accrual is slower than expected and at least 50 patients reach one year of follow-up while total accrual is still fewer than 100 patients, then barriers to accrual will be reconsidered and corrective measures taken. We will also evaluate our event rate at that time to determine whether our 95% confidence interval will satisfactorily exclude the unacceptable event rate of 50% set forth a priori (see sample size justification – Section F.c.), understanding that our limited sample size in this situation may limit statistical power and result in an unacceptably wide confidence interval.

**Study Duration, Completion or Termination.**

Criteria for Removal of Patients from the Study.

Patients will be removed from protocol for any of the following:

1. Withdrawal of consent for any reason.
2. Inability to comply with study procedures.
3. Any illness that prevents treatment continuation, or interferes with treatment
4. If PI and/or subject decides to discontinue treatment for reason(s) other than an AE
5. Death, or subject is lost to follow-up
6. At PI's discretion.

Study Duration.

We estimate it will take approximately 2 years to complete enrollment for this study. Along with the 5 year QOL questionnaire, the total duration of the study is estimated to take approximately 7.5 years.

**F. Data Analysis Plan:**

(a) Definition of primary endpoint: Composite endpoint of six binary outcomes at one year. These are defined below with an estimated composite event rate of 40%. Each event will count equally, and a composite event will be scored only once per patient.

1. lymphedema – an increase in inter limb arm circumference of at least 10% in the lower arm or the upper arm, or both, compared with the contralateral arm at the same time point, will be judged to be clinically significant lymphedema. Arm circumference 15 cm above the medial epicondyle (upper arms) and 15 cm below the medial epicondyle (lower arms) will be measured at 6, 12, 36, and 60 months by clinicians.
2. shoulder stiffness – reported by patient questionnaire [EORTC QLQ-C3014 and breast-cancer module (BR23)].
3. symptomatic rib fracture – diagnosed by evidence of a correlative lesion on plain film or CT.
4. ischemic heart disease – new development of angina with corresponding EKG changes, or myocardial infarction
5. pneumonitis – CTCAE  $\geq$  Grade 2 (requires steroids).
6. brachial plexopathy – CTCAE  $\geq$  Grade 2 (symptomatic, limits ADLs).

(b) Definition of secondary outcomes/endpoints:

1. axillary recurrence – Recurrent disease presentation within axillary lymph node levels I, II, or III. Note that supraclavicular region is not included in this endpoint as in AMAROS historically.

2. local-regional failure free survival – time from date of enrollment to earlier of clinical detection of any ipsilateral recurrent disease to the breast/chest wall or regional lymph nodes (levels I, II, III, supraclavicular, and internal mammary lymph nodes) or death.
3. distant metastasis-free survival – time from date of enrollment to earlier of clinical detection of metastatic disease beyond the breast/chest wall and regional lymph nodes or death.
4. overall survival – time from date of enrollment to date of death from any cause.
5. quality of life [EORTC QLQ-C3014 and breast-cancer module (BR23)].

(c) Analytic plan for primary objective: This analysis will be performed after all patients have been entered and followed for a minimum of one year. All eligible patients (as defined above) that begin protocol treatment will be included in the analysis.

A non-inferiority margin of 10% was chosen after extensive consultation with multiple radiation oncologists. Note this margin is an absolute difference between the toxicity event rate of standard treatment (assumed to be 40%) and that of proposed treatment, where a higher rate indicates treatment is more toxic. The sample size calculation is based powering the study with 80% power and 5% significance level. The sample size is dependent on the actual absolute difference between the toxicity event rate of standard treatment and that of the proposed treatment. When it is assumed that the actual toxicity event rate of proposed treatment is 2% lower (absolute difference) than that of standard care, a total number of 106 patients accomplishes abovementioned power. If less than 44 patients out of 106 are observed to have adverse event, we will conclude that the proposed treatment is non-inferior to standard treatment. Assuming an estimated drop-out rate of 5% of patients lost to follow-up, the calculated total number of patients will be inflated accordingly to 112.

The initial treatment report will contain the following:

1. study accrual rate;
2. tabulation of all cases entered, and any patients excluded from the analysis with reasons for exclusion;
3. distribution of important prognostic baseline variables;
4. compliance rates of treatment delivery with respect to the protocol prescription;
5. observed results with respect to the primary endpoint described above.

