### **IV. Research Methods**

#### **A. Outcome Measure(s):**

Primary Objective:

- Demonstrate the safety and tolerability of adjuvant hypofractionated radiotherapy to the breast (following lumpectomy) or chestwall (following mastectomy), and regionally draining lymphatics.

Secondary Objectives:

- Determine the rates of axillary recurrence, local-regional failure-free survival, distant metastasis-free survival, and overall survival at one and five years.
- Determine the rates of hypothyroidism and reconstruction expander loss/revision.
- Evaluate patient-reported quality of life and body image.

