### ***Exclusion Criteria:***

1. patients  $<18$  years old
2. pregnant women
3. male patients
4. women with T4 disease, including inflammatory breast cancer
5. women who have declined or otherwise not received preceding surgery
6. women with positive margins after primary surgery
7. women with node negative disease

8. women without histologic confirmation of nodal involvement
9. women more than 180 days out from primary breast surgery or adjuvant chemotherapy
10. patients with clinically detected or suspicious lymph node involvement not readily amenable to surgical treatment ( $\geq$ cN2 disease)
11. patients with synchronous bilateral breast cancers
12. patients with prior ipsilateral thoracic or breast radiation
13. patients with distant metastatic disease (cM1) or a life expectancy of less than 5 years
14. active collagen vascular disease, specifically dermatomyositis with a CPK level above normal or with an active skin rash, systemic lupus erythematosis, or scleroderma.
15. other non-malignant systemic disease that would preclude the patient from receiving study treatment or would prevent required follow-up.
16. patients with psychiatric or addictive disorders or other conditions that, in the opinion of the Investigator, would preclude the patient from meeting the study requirements.
17. patients with a separate non-cutaneous cancer diagnosis for which the patient has not been without evidence of disease for at least 5 years

Note: women <50 years of age, women who received chemotherapy, pN0 (i+ or mol+), and large-breasted women are eligible for enrollment.

These criteria were chosen to include most women with pathologic lymph-node positive disease who have undergone surgery for breast cancer. Women without node-positive disease were excluded as there is already Level I evidence supporting the use of hypofractionation for those women. Women with inflammatory breast cancer were excluded given the extreme biologic aggression of such malignancies and the general desire of the treatment team in general to maximize therapeutic intensity, at times including escalated radiation doses that may increase magnitude of expected toxicity.

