**D. Schedule of Study Assessments:**

Study Visits	Screening	Treatment-Phase				Follow Up			
		Radiation On-Treatment Visits 				FU 6 Months	FU 12 Months	FU 36 Months	FU 60 Month
Visit Window	-28 days	Week 1	Week 2	Week 3	Week 4 	± 30 days from RT end	± 30 days from RT end	± 60 days from RT end	± 60 days from RT end
Procedures									
Informed consent	X								
Pregnancy Test (if premenopausal)	X								
Confirm eligibility (Inclusion/exclusion criteria)	X								
Medical history	X					X	X	X	X
Physical Exam (including weight) 	X					X	X	X	X
Height	X								
ECOG performance status	X	X	X	X	X	X	X	X	X
Vital Signs (blood pressure, pulse, respiratory rate, temp,)	X	X	X	X	X				
Lymphedema measurement	X					X	X	X	X
Shoulder mobility measurement 	X					X	X	X	X
Radiation		X	X	X	X				
Prior and concomitant medications	X	X	X	X	X	X	X	X	X
Adverse events	X	X	X	X	X	X	X	X	X
TSH	X						X	X	X
Mammogram 							X		
EORTC QLC-C30 questionnaire	X					X	X	X	X
BR.23 questionnaire	X					X	X	X	X

1. This encounter should include a focused physical exam to include, at minimum, a bilateral breast/chest wall, lymph node, and upper extremity exam, including weight.
2. All toxicity noted by the study clinicians should be documented at baseline, during weekly visits while receiving radiation, and at each per-protocol follow-up visit (6, 12, 36, and 60 months).
3. Clinicians should use a goniometer to measure *bilateral* shoulder mobility in four excursions: abduction, adduction, ante version, and retroversion.
4. Mammography for any remaining intact breast should be performed annually or as clinically indicated.
5. If applicable.
6. 15 treatments ± 4 additional fractions as a boost.

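### The only analysis set for the primary toxicity endpoint leaves out treated women found ineligible, with no all-treated analysis and no deadline or blinding for eligibility rulings

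*Combined protocol and SAP*

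**What the plan says.** The primary objective (section A, Outcome Measures) is safety and tolerability, and the primary endpoint (section F(a)) is a six-part toxicity composite at one year in a single arm. Section F(c) defines one analysis set for it: "All eligible patients (as defined above) that begin protocol treatment will be included in the analysis". Being eligible is thus a second condition on top of starting treatment. On timing, the same paragraph says: "This analysis will be performed after all patients have been entered and followed for a minimum of one year".

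The plan expects some exclusions. The initial treatment report is to contain a "tabulation of all cases entered, and any patients excluded from the analysis with reasons for exclusion". No all-treated set and no sensitivity analysis is described anywhere.

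Eligibility is confirmed at screening (section D, Schedule of Study Assessments). It comes up again in the list of tasks for routine on-site monitoring: "Subject source documentation verification and subject eligibility". Those visits take place every 8-12 weeks, while the radiation course lasts 3-4 weeks (section E, Description, Risks and Justification). Toxicity is recorded as treatment proceeds: "All toxicity noted by the study clinicians should be documented at baseline, during weekly visits while receiving radiation", and again at the follow-up visits.

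**The concern.** The question the trial asks is how toxic this treatment is. A woman who received it tells us something about that whether or not an entry criterion was met. Leaving her out of the primary count discards safety evidence, and there is no control arm in which similar exclusions might offset the effect.

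The plan also leaves the timing of the eligibility decision open. A ruling can come after treatment and after toxicity has been recorded, by people who can see it. Nothing requires it to be made by a set date or from baseline data alone. The printed success rule is a count of events, so excluding a woman with an event lowers the count, while excluding a woman without one leaves it unchanged. A few rulings in one direction could decide a close result.

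**Working it through.** **Inputs.** From section F: reference rate 40%, margin 10 points, assumed true rate 38%, 80% power, 5% significance, success if fewer than 44 of 106 have an event, 5% loss to follow-up. From the Accrual paragraph of Potential Scientific Problems: unacceptable rate 50%. The documents give no number of treated-but-ineligible women, so the figures for them below are assumptions.

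**1. The plan's own figures.** One-sample proportion, normal approximation, one-sided 5%:

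n = [1.645 × √(0.5 × 0.5) + 0.842 × √(0.38 × 0.62)]² / 0.12² = 105.2, rounded up to 106.

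106 / 0.95 = 111.6, rounded up to 112. Both reproduce. The inflation covers loss to follow-up only and makes no allowance for ineligible patients.

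**2. The cut-off in exact terms.** With X ~ Binomial(106, 0.5), P(X ≤ 43) = 0.0322, P(X ≤ 44) = 0.0491 and P(X ≤ 45) = 0.0724. So 45/106 fails both the printed rule and an exact one-sided 5% limit (44).

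**3. Two event patients excluded.** 45 − 2 = 43 events in 106 − 2 = 104 women. The printed count is met. For n = 104 the exact 5% limit is also 43, with P(X ≤ 43) = 0.0475. The reversal is therefore not an artefact of applying a 106-patient cut-off to 104 patients.

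**4. The same check from the other side.** Suppose 43/106 eligible women have events, which passes. Adding one treated-but-ineligible woman with an event gives 44/107 (exact limit 44), which still passes. Adding two gives 45/108 (exact limit 44), which fails.

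**5. False-success probability, worst case.** The true rate is 50% among 106 treated women, and k women, all with events, are excluded. The probability is P(X ≤ c + k), where c is the cut-off used.

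| k | c = 43 as printed | c = exact 5% limit for 106 − k |
|---|---|---|
| 0 | 0.032 | 0.049 |
| 1 | 0.049 | 0.049 |
| 2 | 0.072 | 0.072 |
| 3 | 0.103 | 0.072 |
| 5 | 0.191 | 0.103 |

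**6. A less extreme assumption.** Let a share s of treated women be ineligible with event rate r, and keep the all-treated rate at 50%. The eligible rate is then (0.5 − s·r)/(1 − s). With 106 eligible women analysed and the cut-off at 43, the false-success probability is:

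| s | r = 50% | r = 70% | r = 90% |
|---|---|---|---|
| 2% | 0.032 | 0.039 | 0.046 |
| 5% | 0.032 | 0.051 | 0.078 |
| 10% | 0.032 | 0.082 | 0.175 |

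If ineligible women have the same event rate as the others (r = 50%), there is no bias at any share.

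**7. Direction.** If the cut-off is reset to the number analysed, exclusions can also work against the treatment. 44/106 meets the exact limit of 44; excluding one woman without an event gives 44/105, against a limit of 43, and fails.

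**The case against.** The strongest reply is that the set is prespecified and refers to baseline criteria checked before radiation starts. Few women should pass screening and later prove ineligible. No section orders or schedules an eligibility ruling after treatment.

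The monitoring schedule is also weak evidence for outcome-aware exclusion. After baseline, arm circumference and the questionnaire item on shoulder movement are first collected at 6 months from the end of radiotherapy. A visit every 8-12 weeks would usually come before either component can be scored. Earlier events such as pneumonitis could precede a review, and the plan does not say that every chart is checked at the next visit, so a late ruling remains possible.

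Many criteria leave little room for judgement after the fact. The 180-day limits are date calculations, and nodal status is read from pathology. The exclusion of "women with node negative disease" beside the admission of some ypN0 and pN0 (i+ or mol+) patients is a wording problem that should be reconciled in its own right.

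The reversal example is an edge case. It needs exactly 45 events, and both excluded women must have had one. If two of the 106 were excluded at random, the chance of that is (45 × 44)/(106 × 105) = 18%. With a single exclusion from 45, 44 events remain and the printed rule still fails.

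Finally, exclusions are tabulated with reasons, and serious-event reporting and the six-monthly reports to the Data and Safety Monitoring Committee are not restricted to eligible patients.

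All of this limits the likely size of the effect. It does not change the analysis set. The table of exclusions and the safety reports make these women visible but do not return their events to the primary count.

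**Conclusion.** The point stands as a gap in the primary safety analysis: the only defined set leaves out treated women found ineligible, and the plan neither limits when that finding may be made nor keeps it separate from the outcome.

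A reader might infer more: that women are dropped once their toxicity is known, or that the rule biases the trial towards non-inferiority. The documents do not support either reading. They permit late rulings but do not direct them. They give no data linking entry breaches to toxicity, and exclusions unrelated to toxicity would leave the expected event rate unchanged.

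The size is therefore conditional. In the worst case, two excluded event patients (2/106, about 2% of those treated) are enough to change the conclusion or to take the false-success probability from 0.032 to 0.072 under the printed cut-off. With one such patient it stays just under 5%. These figures assume an exact one-sided test against 50% and that every excluded woman had an event. The change is worth making because it is cheap and removes the dependence on eligibility rulings.

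**What to change.** Replace the sentence in section F(c) with wording such as: *All patients who receive at least one fraction of protocol radiotherapy will be included in the primary analysis, whatever is later found about their eligibility.*

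Keep the eligible-only set as a named sensitivity analysis. State that eligibility for it is judged on baseline data, without sight of the composite outcome, and finalised before the primary analysis. The planned table of exclusions can then describe that sensitivity set.

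The cost is one sentence and one additional results table. The planned numbers (106 evaluable, 112 enrolled) do not change. The small downside is that a few protocol violators enter the primary set; the sensitivity analysis shows whether they matter.
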